4.1.1.3 Supplementary Analyses

Primary endpoint data will moreover be summarized by randomized treatment group using descriptive statistics for metric variables (see beginning of Section 4.1) on the FAS-UP (OC) and on the PPS (OC).

4.1.2 Secondary Endpoints

4.1.2.1 Key Secondary Efficacy Endpoints

The two key secondary efficacy endpoints are defined in Section 2.2.1.2.1 and will be derived as follows:

- The value of the respective TETRAS score (TETRAS Performance dominant UL score and TETRAS ADL UL score) will be calculated for study baseline¹⁴ and for Week 6 (V4) as sum of all corresponding items as defined in Appendix 8.1 (see scores no. 5 and no. 2, respectively).
- Change from study baseline¹⁴ to Week 6 (V4) will be calculated by subtracting the value of the respective TETRAS score at study baseline from the respective value at Week 6 (V4), derived as described above.
- In case an item belonging to the respective TETRAS score is missing, the respective TETRAS score value cannot be meaningfully derived for the affected visit. Hence, derivation of each of the two key secondary endpoints requires that answers to all items belonging to the respective TETRAS score are available at both study baseline and Week 6 (V4). Otherwise, the respective key secondary endpoint will not be calculated and considered as missing.

The two key secondary efficacy endpoints will be tested with ANCOVA models similar to that for the primary analysis of the primary endpoint (see Section 4.1.1.1). However, the study baseline of the analyzed TETRAS score [i.e., TETRAS Performance dominant UL score (Score no. 5 in

¹⁴ For definition of study baseline see beginning of Section 4.

[Appendix 8.1](#)) or TETRAS ADL UL score (Score no. 2 in [Appendix 8.1](#)), as applicable] will be used for baseline adjustment. Handling of multiplicity is addressed in Section [4.7.2](#).

Missing data handling, pooling of study sites, exploratory sensitivity analyses (Section [4.1.1.2](#)), and supplementary analyses (Section [4.1.1.3](#)) will also be handled analogously to the respective analyses of the primary endpoint. For ANCOVA-based sensitivity analyses, the respectively analyzed TETRAS subscale score (see above) will be used. The multiple imputation based sensitivity analysis was planned to be performed in case of more than 10% missingness on the respective key secondary endpoint among all treated subjects. During the DRM performed on 17Jan2024 under double blind conditions, the two key secondary efficacy endpoints were found to be completely available for all treated subjects. It was hence concluded that multiple imputation is not required for key secondary endpoints.

4.1.2.2 Other Secondary Efficacy Endpoints

Other secondary endpoints are defined in Section [2.2.1.2.2](#). TETRAS based endpoints will be derived analogously as described in Section [4.1.2.1](#) for the two key secondary efficacy endpoints (see also [Appendix 8.1](#) for assignment of TETRAS items to the different TETRAS scores). This requires that answers to all respective items are available. No missing value replacement will be performed for any other secondary efficacy endpoint. Inferential statistical results reported for other secondary efficacy endpoints will be interpreted only descriptively.

Unilateral treatment period:

Other secondary endpoints of the unilateral treatment period will be analyzed by applying ANCOVA models similar to that for the primary analysis of the primary endpoint (see Section [4.1.1.1](#)). However, for TETRAS subscales, the study baseline of the analyzed TETRAS (subscale) score will be used for baseline adjustment. For GICS by investigator and GICS by subject, the study baseline of the TETRAS ADL subscale score will be used for baseline adjustment. The same statistics as defined in Section [4.1.1.1](#) will be reported.

Furthermore, descriptive statistics for metric variables will be provided by treatment group.

Bilateral treatment period:

Other secondary endpoints of the bilateral treatment period all belong to Category A, (see Section [4.1](#)). They will be analyzed by applying ANCOVA models similar to that for the primary analysis of the primary endpoint (see Section [4.1.1.1](#)). However, the Cycle 2 baseline of the analyzed variable will be used for baseline adjustment.

Since all subjects will receive the same active treatment (NT201) in Cycle 2, it is not intended to test the effect of treatment for any other secondary endpoint from the bilateral treatment period.

Rather, the above mentioned ANCOVA models will be used to estimate the average changes from Cycle 2 baseline by LS Means and respective 95% confidence intervals.

SAS code similar to the statements provided in Section [4.1.1.1](#) will be used. Only the LSMeans statement will be adapted as follows because the LS Mean treatment difference is not needed:

```
LSMEANS TRT01P / OM CL alpha=0.05;
```

The following statistics will be displayed:

- n (number of observations used in the analysis)
- p-values of fixed class effects (randomized treatment group and study site) and the fixed continuous covariate (baseline severity level of the respectively analyzed variable)
- LS Mean per treatment group with associated SE and 95% CI.

Furthermore, adequate descriptive statistics will be provided for the “total active” treatment group in Cycle 2 and by randomized treatment group.

4.1.3 Other Efficacy Endpoints

- Derived other efficacy endpoints will be computed as follows:
 - Endpoints based on assessments of angular tremor amplitude [deg] in the unilateral treatment period:
 - For the task with maximum amplitude at study baseline, derivations will be performed as follows:
 - The task with maximum amplitude at study baseline at wrist level will be determined by performing steps 1 to 3 for calculation of the primary efficacy endpoint (see Section 4.1.1.1). The same approach will be applied for selection of the task with maximum amplitude at study baseline at elbow and shoulder levels.
 - For the respectively selected task, the angular tremor amplitude at wrist/ shoulder/ elbow level will be derived analogously, i.e. as arithmetic mean of the combined RMS (see Steps 1 and 2 in Section 4.1.1.1) for each post-baseline visit in Cycle 1 [RMS deg].
 - Changes from study baseline to all post-baseline visits in Cycle 1 at wrist/ elbow/ shoulder level will be derived as described for wrist level at Week 6 (V4) [RMS deg] in Section 4.1.1.1.
 - Note: In case the task with maximum amplitude at wrist/ shoulder/ elbow level at study baseline cannot be derived due to missing or incomplete assessments of tremor amplitude at corresponding level at study baseline, respective values and changes from study baseline at any post-baseline visits cannot be derived either and will as well be considered as missing. This applies regardless of whether TremorTek assessments wrist level are completely available at Week 6 (V4) or not.
 - For the maximum tremor amplitude from Tasks I to IV [RMS deg], steps 1 to 3 as for calculation of maximum tremor amplitude at wrist level at study baseline (see Section 4.1.1.1) will be performed. The selection of the task with the maximum arithmetic mean (step 3) will be performed separately for each visit and for each level (wrist/elbow/shoulder). I.e., for calculation of values and changes from study baseline, only the task with maximum tremor amplitude at respective visit will be considered.
 - For the mean amplitude of Tasks I to IV [RMS deg], step 1 and step 2 as for calculation of maximum amplitude (see Section 4.1.1.1) will be performed whereby for the calculation of RMS respective measurements of wrist, elbow or shoulder will be used. The mean of the four tasks will be calculated (rounded by five decimals). In addition to values, changes from study baseline will be calculated.
- Endpoints based on assessments of angular tremor amplitude in the bilateral treatment period will be derived analogously as described above for respective endpoints for the unilateral treatment period, but separately by motor dominant/ non-dominant UL as well as for the difference between both ULs. For all post-baseline visits in Cycle 2, changes will be derived as both changes from study baseline¹⁵ and as changes from Cycle 2 baseline for

¹⁵ For definition of study baseline see beginning of Section 4.

the motor dominant UL, as applicable. Changes from study baseline are only derived for motor-dominant UL because, in accordance with the visit schedules for treatment Cycles 1 and 2 in the CSP (see Tables 5 and 6), angular tremor amplitude of motor-dominant UL was only assessed in Cycle 2, i.e., no study baseline is available for the non-dominant UL.

- As defined in Section 4.1.1.1 for the primary efficacy endpoint, derivation of endpoints based on assessments of tremor amplitude generally requires that all respective assessments are available. Otherwise, the affected endpoint will be considered as missing.
- TETRAS based endpoints:
 - Endpoints based on TETRAS Performance by investigator and TETRAS ADL will be derived analogously as described in Section 4.1.2.1 for the two key secondary efficacy endpoints (see also Appendix 8.1 for assignment of TETRAS items to the different TETRAS scores).
 - Endpoints based on TETRAS Performance assessments by IRP: Values will be derived as medians over all available scores from IRP members: First, the respective TETRAS score (Score no. 5 in Appendix 8.1) will be calculated for each IRP member. Second, the median over the respective TETRAS score from all IRP members will be computed and rounded by 3 decimals whereby median will only be calculated if score is available for at least 2 out of 3 IRP members. Changes from study baseline will be calculated based on these medians.
 - As TETRAS based endpoints will only be calculated if answers to all respective items are available.
- Endpoints based on QUEST dimension and total scores:
 - This patient-reported outcome questionnaire has 30 items that inform on interference and impact of ET on five dimensions of QoL: Physical (9 items: items 13-21), Psychosocial (9 items: items 22-30), Communication (3 items: items 1-3), Hobbies/Leisure (3 items: items 10-12), and Work/Finance (6 items: items 4-9). Most items have 5-point frequency response scale ranging from 0 ('Never') to 4 ('Always'). For the items 6, 7, 11, and 12 a 'No' or 'Yes' response is asked for (scored as 0 or 4, respectively). Some items (4, 5, 7, 8, 14) have an additional answer option "Not applicable" (no score assigned, "not applicable" items will not be considered for analysis). The QUEST scores on the five dimensions/domains are each calculated based on applicable items¹⁶ only and expressed as a percentage of the total score possible for the respective dimension/domain, ranging from 0 to 100 (rounded by two decimals).
 - Each dimension score is hence calculated as the sum of scores for all applicable items of the respective dimension divided by the sum of possible points (=number of applicable items * 4) of the respective dimension.
 - The total score (summary index) is calculated as the mean of the five domain scores, also ranging from 0 to 100 (rounded by two decimals). A higher score represents higher dissatisfaction with health-related QoL and disability.
 - In addition to values per visit, changes from study baseline will be calculated for applicable Cycle 1 and Cycle 2 visits and changes from cycle baseline additionally for Cycle 2.

¹⁶ Applicable items = items for which another response option than "not applicable" was chosen

- QUEST scores and respective changes from study / Cycle 2 baseline will only be calculated if answers to all respective (and applicable) items are available.

○

All above-mentioned changes from study/ Cycle 2 baseline (defined at beginning of Section 4) will be derived by subtracting the study/ Cycle 2 baseline value from the respective post-baseline value.

No missing value replacement will be performed for any other efficacy endpoint.

All other efficacy endpoints will be analyzed by descriptive statistics only.

4.2 Pharmacodynamic Analyses

Not applicable.

4.3 Pharmacokinetic Analyses

Not applicable.

4.4 Pharmacogenetic Analyses

Not applicable.

4.5 Safety Analyses

All safety analyses for Cycle 1 will be performed by actual treatment group on SES-UP. All safety analyses for Cycle 2 will be performed on the SES-BT, by actual treatment group in Cycle 1 and in total. All safety analyses for the total observation period will be performed on SES-UP, by actual treatment group in Cycle 1 and in total.

For calculation of TEAE based incidence rates, the denominator will be the number of subjects in the respective analysis set, by actual treatment group or in total (as applicable).

AEs will be coded according to the Medical Dictionary for Regulatory Activities [MedDRA] version that is in effect at the time the database is closed.

Only TEAEs will be analyzed, which are defined as AEs with onset or worsening after the first administration of the IP. For details on separation of TEAEs and non-TEAEs see [Appendix 8.5](#).

If in case of a public health emergency, e.g. due to a COVID-19 outbreak, the second injection visit V8a of Cycle 2 is performed later than 25 weeks after the first injection visit V2 the AEs

¹⁷ Health state = pattern of scores over the five dimensions, e.g., 13333 for a subject indicating slight problems in mobility and severe problems on the other four dimensions.

starting or worsening later than 25 weeks after baseline visit V2 of Cycle 1 and before injection at V8a of Cycle 2 are treated as non-TEAEs.

If an AE worsens between start and end of this AE, it will be considered as new AE entry with a new record in the SDTM dataset starting with the date of the worsening (start of new AE = worsening date, stop date of milder AE episode = date of AE worsening).

For analysis, incompletely recorded or completely missing start of AEs will be estimated according to rules laid down in [Appendix 8.6](#). End dates will not be imputed. In the AE listing, start date as recorded and as imputed for analysis will be displayed.

Calculation of time to onset/duration of AEs (days):

- Time to onset of an AE is defined as start date of AE - date of first administration of study drug in respective treatment cycle [+ 1 day for TEAEs]
- The duration of an AE will be calculated as stop date - onset date + 1 day. The duration of an AE will be missing if no AE stop date is provided

Treatment-relatedness of AEs will be determined based on the assessment of the investigator.

If a subject has more than one intensity/ causal relationship to treatment/ outcome within a preferred term (PT) only the worst intensity/ causal relationship to treatment/ outcome will be considered for calculation of incidence rates in the frequency tables reporting incidences by intensity/ causal relationship to treatment/ outcome. Similarly, for the analysis overall, i.e., for subjects with at least one TEAE, only the worst intensity/ causal relationship to treatment/ outcome category per subject will be counted for calculating incidence rates.

The worst outcome is defined in the following order (worst outcome to best outcome):

- fatal
- unknown
- not recovered/not resolved
- recovering/resolving
- recovered/resolved with sequelae
- recovered/resolved.

Relationship to COVID-19 disease is documented in eCRF. Furthermore, the medical coding specialist will check if further AEs could be related to COVID-19 disease (but also consider information from eCRF). The medical coding specialist will classify all AEs as related/ suspected/ not related to COVID-19 disease. Both kinds of information will be added in SDTMs and displayed in by-subject data listings of AEs. For analysis and the listing of TEAEs related to COVID-19 disease, information from coding specialist will be used, whereby “suspected” AEs will be regarded as related to COVID-19 disease.

The AEs listed in [Table 1](#) are defined as adverse event of special interest (AESIs) for this study.

Table 1: List of Adverse Events of Special Interest Possibly Indicating Toxin Spread

| MedDRA Preferred Term | MedDRA Preferred Term |
|---|------------------------------|
| Accommodation disorder | IIIrd nerve paresis |
| Areflexia | Ileus paralytic |
| Aspiration | IVth nerve paresis |
| Botulism | Monoparesis |
| Bradycardia | Muscular weakness |
| Bulbar palsy | Paralysis |
| Constipation | Paraparesis |
| Cranial nerve palsies multiple | Paresis |
| Cranial nerve paralysis | Paresis cranial nerve |
| Diaphragmatic paralysis | Peripheral nerve palsy |
| Diplopia | Peripheral paralysis |
| Dry mouth | Pelvic floor muscle weakness |
| Dysarthria | Pneumonia aspiration |
| Dysphagia | Pupillary reflex impaired |
| Dysphonia | Quadriparesis |
| Dyspnoea | Respiratory arrest |
| Extraocular muscle paresis* | Respiratory depression |
| Eyelid function disorder | Respiratory failure |
| Eyelid ptosis | Speech disorder |
| Facial paralysis | Trigeminal nerve paresis |
| Facial paresis | Urinary retention |
| Hemiparesis | Vision blurred |
| Hypoglossal nerve paresis | Vocal cord paralysis |
| Hyporeflexia | Vocal cord paresis |
| Hypotonia | |
| *LLT Extraocular muscle paresis, PT: Ophthalmoplegia Wording of terms is according to MedDRA version 26.1. | |

TEAEs of Cycle 1 are defined as TEAEs with onset or worsening before date and time of administration of IP at V8(a). For subjects who do not receive study treatment during Cycle 2 all TEAEs will be considered as TEAEs of Cycle 1. TEAEs of Cycle 2 are defined as TEAEs with onset or worsening on or after date and time of the administration of IP at V8(a).

In case of missing intensity or missing causal relationship of an AE to treatment, the worst-case principle will be applied, i.e., a missing intensity will be set to “severe” and a missing causal relationship will be set to “related”. Missing outcome will be set to “unknown”.

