Since the first observation of possible efficacy of *BoNT A* in the indication of ET [Jankovic 1991], little research has been conducted into this topic. A 2011 update of the American Academy of Neurology treatment guidelines for ET reported that, in the interval since the previous guidelines, new studies providing evidence above Class IV on the efficacy or safety of *BoNT A* for the treatment of ET had not been conducted [Zesiewicz 2011]. Consequently, the guidelines continued their assessment of *BoNT A* as a 'Level C, possibly effective' treatment for ET. The same conclusion was reached in another review [Deuschl 2011], which identified only two double-blind placebo-controlled parallel-design studies of *BoNT A* for the treatment of people with essential hand tremor: the afore mentioned Jankovic study [Jankovic 1996] comparing 50 U (plus an optional booster injection of 50 U after 4 weeks) of onabotulinumtoxinA with placebo, and another larger similarly designed confirmatory study [Brin 2001] in which subjects were randomized to either low-dose (50 U) or high-dose (100 U) onabotulinumtoxinA or placebo. Only the wrist flexors and extensors were injected in both these studies, with flexors receiving 60% of the dose and extensors 40%, and patients were followed up for 16 weeks.

In the second trial, the effect of treatment was assessed by clinical rating scales, measures of motor tasks and functional disability, and global assessment of treatment. Hand strength was evaluated by clinical rating and by a dynamometer. While both doses of botulinum toxin type A significantly reduced postural tremor on the clinical rating scales after 4, 6,

12 and 16 weeks, kinetic tremor was significantly reduced only at the 6-week examination. Measures of motor tasks and functional disability were not consistently improved with botulinum toxin type A treatment. Grip strength was reduced for the low- and high-dose botulinum toxin type A groups as compared with the placebo group. Adverse reactions consisted mainly of dose-dependent hand weakness. The authors concluded that *BoNT A* injections for ET of the hands resulted in significant improvement of postural, but not kinetic, hand tremors and resulted in limited functional efficacy. Hand weakness was found to be a dose-dependent significant side effect of treatment at the doses used in this study [Brin 2001]. The ET therapeutic indication development was consequently not further pursued by the sponsor company.

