4.3 Risk-benefit assessment

The existing data on the intramuscular administration of *BoNT A* in general, and of NT 201 in particular, suggest that the treatment to be administered in the current study will not represent a significant risk to the study subjects.

As of October 2019, 25 clinical studies investigating neurological indications have been completed, where a total of 3,987 subjects were exposed to NT 201 in doses up to 800 U per injection session [Wissel 2017]. The neurological and aesthetic study programs have demonstrated the efficacy and safety of NT 201 in various indications. In five clinical studies sponsored by the sponsor, more than 900 adult subjects with UL spasticity have been exposed to NT 201. The total body doses proposed in the current study (up to 165 U per UL, up to 330 U per subject for both ULs) will not exceed the already approved dose for UL spasticity (500 U in the European Union, 400 U in the United States).

The potential benefits of NT 201 in patients with ET have been clearly demonstrated in the placebo-controlled Study MRZ60201-2094-1 [Jog 2017, Merz Pharmaceuticals GmbH 2017], in which significant improvements in FTM Part B motor performance and wrist tremor amplitude were observed, in the absence of treatment-limiting side effects. Adverse drug reactions reported in the NT 201 group were muscular weakness (finger weakness) in two subjects (10.5%) and injection site bruising and injection site pain in one subject each, all of mild intensity. No subject in the NT 201 group had a serious adverse event or an adverse event leading to study discontinuation.

Placebo-treated subjects are expected to receive no objective additional benefit during the unilateral treatment period. However, comparison with a group of subjects treated with placebo allows the most scientifically reliable conclusions on the effect of the investigational drug. To reduce the required overall number of subjects exposed to placebo, a 2:1 randomization is foreseen. Furthermore, during the bilateral treatment period, all subjects, including those who previously received placebo, will receive NT 201. Thus, all subjects who continue into the bilateral treatment period are expected to receive therapeutic

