9.1.1.3.1 Adverse events

AEs will be recorded in source documents after the ICF has been signed and will be recorded in the eCRF at all successive visits.

Subjects are requested to report all AEs to the investigator or site staff. It is the obligation of the investigator to detect AEs by questioning the subject at each visit. At the injection visits, AE questioning will be done twice; first before injection and the second assessment will be performed about 30 minutes after injection. All AEs observed throughout the course of the study are to be documented in the subject file and in the eCRF. This equally applies to AEs during the period of a potential COVID-19 related temporary halt. For definitions and details regarding documentation and reporting of AEs, see [Sections 10.1 to 10.3](#).

Subjects will be actively questioned and closely monitored for signs of potential toxin spread as indicated by specific AESIs, defined by the European Medicines Agency and FDA, see [Section 10.3](#) and [Table 7](#). The investigator or delegate must actively question each subject for AESIs, see [Section 10.3](#) and [Table 7](#), at each visit, beginning at the study baseline visit (V2) before injection and approximately 30 minutes after injection. Questioning at baseline before injection is done to identify possible concomitant diseases which have not been recorded as medical history. The questioning and documentation of answers will be standardized.

If any contact with the subject identifies an (S)AE/AESI that needs confirmation or treatment, (e.g. respiratory disorder, dyspnea, aspiration, dysphagia, speech disorder, dysphonia, other signs of bulbar palsy, or botulism) the investigator must schedule an extra visit as soon as possible after the contact. If such an extra visit is not possible in case of a public health emergency, e.g. due to a COVID-19 outbreak, it is up to the medical

judgement of the investigator to decide whether referral to a specialist or emergency care is necessary for further treatment and confirmation.

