 - Overall summary of TEAEs, displaying incidences of TEAEs (in total / related to treatment), TEAEs (in total / related to treatment), serious TEAEs (in total / related

- to treatment, TEAEs leading to premature study discontinuation (in total / related to treatment), fatal TEAE (in total / related to treatment) and TEAEs related to COVID-19
- TEAEs, subjects with TEAEs and number of TEAEs by MedDRA SOC and PT
 - TEAEs, subjects with TEAEs by PT
 - TEAEs by worst intensity, subjects with TEAEs
 - TEAEs by worst causal relationship, subjects with TEAEs
 - TEAEs by worst outcome, subjects with TEAEs
 - Serious TEAEs, subjects with serious TEAEs and number of serious TEAEs by SOC and PT
 - Non-serious TEAEs, subjects with non-serious TEAEs and number of non-serious TEAEs by SOC and PT
 - Treatment-related non-serious TEAEs
 - TEAESIs, subjects with TEAESIs and number of TEAESIs by SOC and PT
 - Treatment-related TEAESIs
 - The following by-subject listings of TEAEs occurring in the total observation period will be generated for Section 14.3 of the CSR and include information on treatment cycle:
 - Serious TEAEs, listing of subjects
 - Deaths, listing of all serious TEAEs leading to death
 - TEAEs leading to premature study discontinuation of study, listing of subjects
 - TEAEs of special interest, listing of subjects
 - TEAEs related to COVID-19, listing of subjects.
 - In addition, a complete listing of all AEs (TEAEs and non-TEAEs) occurring in the total observation period will be provided for CSR Section 16.2, also including information on treatment cycle for TEAEs.
- HHD maximum grip strength: Descriptive statistics for HHD maximum grip strength [Newton] (values and changes from applicable cycle baseline, i.e., study baseline for Cycle 1, Cycle 2 baseline for Cycle 2) will be provided by visit for both injection cycles.
 - For Cycle 1, the above-specified analyses will be performed only for treated UL, irrespective of whether the motor dominant UL (acc. to CSP) or the non-dominant UL was treated. Data for non-injected UL will be listed. Furthermore, the intra-individual difference of changes in maximum grip strength from study baseline between hand of treated and hand of untreated UL will be analyzed. The difference will be derived as change from study baseline at hand of injected UL – change from study baseline at hand of non-injected UL.

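### AESI totals and the weakness and paresis rows mix expected local weakness in the injected arm with possible remote toxin spread

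*SAP*

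**What the plan says.** SAP 4.5 states that the events in its Table 1 "are defined as adverse event of special interest (AESIs) for this study", and the table is titled "List of Adverse Events of Special Interest Possibly Indicating Toxin Spread". It holds 49 terms. One is "Muscular weakness"; others are Paresis, Monoparesis, Paralysis, Peripheral paralysis, Peripheral nerve palsy, Hypotonia, Hyporeflexia and Areflexia. No condition on body site or side is attached to any of them. Protocol 9.1.1.3.1 gives the AESIs the same purpose: subjects are watched for "signs of potential toxin spread as indicated by specific AESIs".

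The planned output in SAP 4.5.3 is "TEAESIs, subjects with TEAESIs and number of TEAESIs by SOC and PT", for the total observation period and for each cycle, plus a treatment-related version and a by-subject listing.

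On local weakness, Protocol 4.1.3 describes the product as acting by local, slowly reversible paralysis. For an earlier botulinum toxin trial, Protocol 4.1.2 reports: "Adverse reactions consisted mainly of dose-dependent hand weakness". Protocol 4.2 says wrist weakness often compromised efficacy in earlier studies. Protocol 8.2.2 gives differing susceptibility of muscles to weakness as one reason for flexible forearm dosing. For the sponsor's predecessor study, Protocol 4.3 lists "muscular weakness (finger weakness) in two subjects (10.5"%), all mild.

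Protocol 12.4.5 says that safety endpoints will be analysed by period and, where that fits, by upper limb.

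**The concern.** A term-only definition suits capture and expedited reporting, where breadth is wanted. It is less suitable as a summary measure when one listed term is also a known effect of the drug at the place where it is injected. Mild finger weakness in the injected hand and new weakness in a leg would both be coded to Muscular weakness, fall in the same row and add equally to the TEAESI total.

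Safety against placebo in the unilateral period is a secondary objective (Protocol 5). An excess of TEAESIs on NT 201 could be read as a spread signal when it is local weakness. Conversely, a remote weakness event would not stand out from local ones within its row. The question is sharper in Cycle 2, where both arms are injected and no untreated arm remains for comparison.

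**Working it through.** **1. Can the planned tables separate the two kinds of event?**

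- *Coded term.* Partly. Separate rows already isolate bulbar, ocular, respiratory and autonomic terms. Nine terms say nothing about site: Muscular weakness, Paresis, Monoparesis, Paralysis, Peripheral paralysis, Peripheral nerve palsy, Hypotonia, Hyporeflexia and Areflexia. That leaves 49 − 9 = 40 rows largely unaffected.
- *Relatedness.* No. Protocol 10.1.2 calls an event related when a causal link to the product is a reasonable possibility. That covers local weakness and spread alike.
- *Limb.* No. The SAP reports exposure and grip strength by treated limb (SAP 4.5.3) but does not do so for adverse events. SAP section 6 does not mention leaving out the protocol's by-limb provision.
- *Recorded data.* The adverse event items in Protocol 10.1 include no field for site or side. Location can enter only through the reported term, the comment or the AESI form.

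**2. How many subjects might this affect?**

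Inputs: 2 subjects and 10.5% (Protocol 4.3); predecessor size n = 30 (Protocol 4.1.2); about 50 subjects planned on NT 201 (Protocol 7.1).

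The denominator is not stated. 2/18 = 11.1%, 2/19 = 10.5% and 2/20 = 10.0%, so only 19 reproduces the printed figure.

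- Exact (Clopper-Pearson) 95% interval for 2/19: 1.3% to 33.1%.
- Expected number in Cycle 1: 50 × 2/19 = 5.3. At the interval limits: 50 × 0.0130 = 0.7 and 50 × 0.3314 = 16.6.
- Chance of at least one case: 1 − (17/19)^50 = 99.6%. At the lower limit: 1 − (1 − 0.0130)^50 = 48%.

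**3. What share of the TEAESI total might be local weakness?**

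This needs the rate *b* of all other AESIs on NT 201, which the documents do not give. Assume values for *b*, and independence between the two kinds of event. With *p* = 2/19, the any-TEAESI incidence is 1 − (1 − p)(1 − b), and the share of counted subjects who have local weakness is p divided by that. For b = 5%: 1 − 0.8947 × 0.95 = 0.150, and 0.1053/0.150 = 70%.

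| Assumed b | Any TEAESI at 2/19 | Share at 2/19 | Share over the 95% interval for p |
|---|---|---|---|
| 2% | 12.3% | 85% | 40% to 96% |
| 5% | 15.0% | 70% | 21% to 91% |
| 10% | 19.5% | 54% | 12% to 83% |

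The share could lie anywhere from 12% to 96%, so the documents show that mixing is likely but not how strongly it dominates.

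**The case against.** Several points on the other side stand.

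- The list is broad by design. Protocol 9.1.1.3.1 attributes the AESIs to the European Medicines Agency and the FDA, and the SAP title says only that the terms possibly indicate spread. There is no case for removing terms.
- TEAESI incidence is one of the other safety endpoints, reported descriptively with no test or decision rule attached.
- A by-subject TEAESI listing is planned. With about five expected cases, location could be judged there if the listing shows it. The output specifications are a separate document (SAP 1.1), so the listing cannot be called deficient.
- Grip strength of the injected hand is compared with the other hand in Cycle 1. Some safety text is redacted, so a further strength measure may exist.

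These points limit the consequence. They do not separate the two kinds of event in the summary tables: grip strength cannot locate a weakness event elsewhere in the body, and a listing does not change the incidence figures.

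A reader might also infer more than the documents support:

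- *That local weakness and spread cannot be told apart anywhere in the tables.* Most rows are specific enough; the problem is confined to the totals and the site-ambiguous rows.
- *That the output tables are headed as toxin spread.* That wording heads the definition list; the planned tables are headed TEAESIs.
- *That a remote event would go unnoticed.* AESIs are asked about at every visit from baseline on and reported within 24 hours on a dedicated form (Protocol 10.3), so case-level recognition is likely.
- *That an excess on NT 201 would be mostly local pharmacology.* This needs background rates that are not given.
- *That weakness in the injected limb is never spread.* Diffusion to a non-injected muscle of the same limb is possible, so the label should not be withdrawn from those events.

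**Conclusion.** The point holds as a reporting weakness. The any-TEAESI and related-TEAESI totals, and the rows for the nine site-ambiguous terms, combine an expected local effect with possible remote spread. Nothing visible in the SAP tables separates them, although the protocol provides for analysis by limb where that fits.

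The likely size is about 5 of 50 NT 201 subjects in Cycle 1, with 0.7 to 16.6 expected over the exact interval for the predecessor rate. This rests on three assumptions: the denominator is 19, the finger weakness was in the treated limb (Protocol 4.3 does not say so), and the rate carries over although predecessor dosing was guided by kinematic measurement and the present dosing is not. Sample size, power and the type I error rate are unaffected.

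**What to change.** In SAP 4.5, before unblinding, add a location classification for every TEAESI coded to Muscular weakness, Paresis, Monoparesis, Paralysis, Peripheral paralysis, Peripheral nerve palsy, Hypotonia, Hyporeflexia or Areflexia. Use three categories: confined to an injected upper limb, elsewhere or generalised, and location unknown. Base it on verbatim terms and AESI forms. The medical coding specialist could do this, as SAP 4.5 already arranges for COVID-19 relatedness.

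In SAP 4.5.3, show the three categories as rows by treatment group and cycle. Give the any-TEAESI and related-TEAESI totals with and without events confined to an injected limb. Leave the AESI list, its label and expedited reporting unchanged.

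The cost is a short blinded review, a few site queries where location is unclear, and a few extra table rows, all for a descriptive endpoint.
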